6.3.2 Efficacy Analysis

The primary evaluation point is overall response at 24 weeks using the NIH cGVHD response criteria measures⁵¹. The overall response score will be assessed as CR, PR, or lack of response as per NIH guidelines. The organ-specific and other subcomponents of the overall response score will be analyzed individually and absolute values recorded.

Up to 2 corticosteroid pulses will be allowed, one for initial flares and one for late flares as described in Section [4.1](#).

Response will be assessed every 12 weeks from the start of baricitinib. To ensure comparability, baseline and on-study methods for response assessment will be performed using identical grading, scale or techniques. The Chronic GVHD Assessment (Clinician) Form will be completed at each 12 week evaluation visit ([Appendix F](#)). Included in that form are both organ-specific primary measurements and clinician-assessed secondary measurements. The response of each affected organ will be evaluated and an overall response will be determined.

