6.3.2.1 Response Criteria

Efficacy will be assessed using NIH consensus criteria measuring for therapeutic response in clinical trials for cGVHD.

- **CR** is defined as resolution of all manifestations in each organ or site
- **PR** is defined as improvement at least 1 organ or site without progression in any other organ or site. The criteria for PR and progression are provided in [Appendix K](#)
- **Lack of Response:** including unchanged, mixed response, and disease progression:
- **Mixed response:** CR or PR in at least 1 organ accompanied by progression in another organ
- **Disease progression:** see [Appendix K](#) for organ criteria
- **Unchanged:** Outcomes that do not meet the criteria for CR, PR, disease progression, or mixed response

As outlined in Section [3.7](#), type of involved organ, location and its measurements will be recorded at scheduled evaluations and reported on the appropriate CRF, equal to “Chronic GVHD Assessment (Clinician) Form,” ([Appendix F](#)). All other measurements not being included in primary assessment but clinically related to cGVHD (e.g., change of pigmentation) will be reported in the source documents.

Skin and skin appendages: Skin assessment will be based on the NIH 0-3 Skin Score, which correlates with cGVHD severity, symptoms, and survival ([Appendix D](#)). Clinician-perceived severity of sclerosis will also be captured on a 0-10 scale. Patient-reported symptoms will be captured on a 0-10 scale and on the Lee symptom scale.

Musculoskeletal connective tissue: Assessment of joint range of motion will be performed by the photographic range of motion (P-ROM) scale and the NIH 0-3 Joint Score, which correlate with changes in joint involvement. In a prior study, both scales performed well but the Joint/Fascia scale better reflected clinical perception of improvement, and the P-ROM better reflected the clinical perception of worsening³³. If these measurements are discrepant, priority

will be given to the NIH 0-3 scale when improvement is detected, and to P-ROM when worsening is detected. If the resolution cannot be achieved then the priority will be given to the NIH 0-3 Joint/Fascia scale, as the P-ROM is of more recent origin and still deemed exploratory in the 2014 NIH cGVHD organ staging recommendations⁴.

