Eyes: The NIH Eye Score uses a scale of 0-3 based on symptoms, need for eye drops, and use of therapeutic procedures or devices. This has been shown to detect improvement of worsening in ocular cGVHD. Patient-reported symptoms will be captured on a 0-10 scale and on the Lee symptom scale.

Mouth: Mouth assessments on the NIH-modified Oral Mucosa Rating Scale (OMRS) include:

- (1) mucosal erythema by 0-3 grading based on the color intensity, (2) lichen-type hyperkeratosis by 0-3 grading based on the percentage of oral surface area, (3) ulceration by 0-6 based on percentage of oral surface area

Gastrointestinal tract: Gastrointestinal (GI) symptoms will be graded through interview by the investigator according to 0-3 severity scales, and weight will be measured at each visit.

Liver: Involvement of liver is graded according to the levels of total serum bilirubin, alkaline phosphatase, and alanine aminotransferase (ALT).

Lung: Absolute percent predicted of the forced expiratory volume in the first second (FEV1), forced vital capacity (FVC), single breath diffusion lung capacity for carbon monoxide (DLCO), total lung capacity (TLC), and residual volume (RV) will be measured on pulmonary function testing (post-bronchodilator response values, as cGVHD of the lungs is not a bronchodilator-responsive process). The %FEV1 will be used for response assessment. Symptoms will be graded through interview by the investigator according to the NIH Symptom Scale 0-3. Slope of %FEV1 will also be measured.

Genitals: Patient-reported symptoms will be captured on a 0-10 scale. **Global chronic GVHD Rating:** The overall clinical impression of patient's cGVHD will be recorded on a 4-point (0-3) scale on the Chronic GVHD Assessment (Clinician) Form.

Chronic GVHD Improvement Scale: The overall changes of patient's cGVHD symptoms during previous 3 months will be recorded on a 7-point (-3 to +3) scale on the Chronic GVHD Assessment (Clinician) Form.

Chronic GVHD Symptom Severity Scale: The overall severity of patient's cGVHD symptoms will be recorded on an 11-point (0-10) numeric scale on the Chronic GVHD Assessment (Clinician) Form.

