6.3.2.2 Summary of Response Measures

- i. Primary response measures
 - 1. Skin: NIH 0-3 Skin Score

2. Joints: P-ROM (1-7 and 1-4) and NIH Joints Fascia Score
 3. Eye: NIH 0-3 Eye Score
 4. Mouth: NIH-modified 0-12 OMRS
 5. GI: GI 0-3 clinician symptom severity scale
 6. Liver: bilirubin, alkaline phosphatase, ALT
 7. Lung: %FEV1
 8. Clinician global assessment scale (3-point, 7-point change, 11-point)
- ii. Secondary assessments
1. Overall response rate at 12 weeks of therapy
 2. NIH organ scoring
 3. Rate of >50% reduction of immunosuppressive therapy at 24 weeks and 48 weeks (steroid pulses on study per section 4.1 will not count towards this assessment)
 4. Overall survival
 5. Platelet count, CRP, C3, C4, albumin
 6. Lee symptom scale, HAP, FACT-BMT
 7. Skin and oral biopsies (if positive at baseline)
 8. MRI (if positive baseline)
 9. Pharmacokinetics
 10. Pharmacodynamic/correlative studies

6.3.2.3 Other endpoints to be recorded at the evaluation time points: Need for secondary systemic therapy for GVHD, malignancy progression, discontinuation of immune suppression, steroid doses, other immunosuppressive drug doses, new topical treatments introduced, intensity of immunosuppression scale, NIH global severity (**Appendix E**), survival, progression-free/malignancy-free survival, disability-free survival.

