APPENDIX K: RESPONSE DETERMINATION FOR CHRONIC GVHD TRIALS BASED ON CLINICIAN ASSESSMENTS

Organ	Complete Response	Partial Response	Progression
Skin	NIH Skin Score 0 after previous involvement	Decrease NIH Skin Score by 1 or more points	Increase in NIH Skin Score by 1 or more points, except 0 to 1
Eyes	NIH Eye Score 0 after previous involvement	Decrease in NIH Eye Score by 1 or more points	Increase in NIH Eye Score by 1 or more points, except 0 to 1
Mouth	NIH Modified OMRS 0 after previous involvement	Decrease in NIH Modified OMRS of 2 or more points	Increase in NIH Modified OMRS of 2 or more points
Esophagus	NIH Esophagus Score 0 after previous involvement	Decrease in NIH Esophagus Score by 1 or more points	Increase in NIH Esophagus Score by 1 or more points, except 0 to 1
Upper GI	NIH Upper GI Score 0 after previous involvement	Decrease in NIH Upper GI Score or more points	Increase in NIH Upper GI Score by 1 or more points, except 0 to 1
Lower GI	NIH Lower GI Score 0 after previous involvement	Decrease in NIH Lower GI Score by 1 or more points	Increase in NIH Lower GI Score by 1 or more points, except from 0 to 1
Liver	Normal ALT, alkaline phosphatase, and Total bilirubin after previous elevation of 1 or more	Decrease by 50%	Increase by 2 x ULN
Lungs	-Normal %FEV1, alkaline phosphatase, and Total bilirubin after previous elevation of 1 or more -If PFTs not available, NIH Lung	-Increase by 10% predicted absolute value of %FEV1 -If PFTs not available, decrease in NIH Lung Symptom	-Decrease by 10% predicted absolute value of %FEV1 -If PFTs not available, increase in NIH Lung Symptom

Organ	Complete Response	Partial Response	Progression
	Symptom Score 0 after previous involvement	Score by 1 or more points	Score by 1 or more points, except 0 to 1
Joints and fascia	Both NIH Joint and Fascia Score 0 and P-ROM score 25 after previous involvement by at least 1 measure	Decrease in NIH Joint and Fascia Score by 1 or more points or increase in P-ROM score by 1 point for any site	Increase in NIH Joint and Fascia Score by 1 or more points or decrease in P-ROM score by 1 point for any site
Global	Clinician overall severity score 0	Clinician overall severity score decreases by 2 or more points on a 0-10 scale	Clinician overall severity score increases by 2 or more points on a 0-10 scale

APPENDIX L: OCCUPATIONAL THERAPY EVALUATION FOR FUNCTIONAL ASSESSMENT, FATIGUE ASSESSMENT, AND UPPER EXTREMITY USE

DISABILITIES OF THE ARM, SHOULDER AND HAND

THE

DASH

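### Appendix K's lung complete-response cell carries liver-test wording that contradicts sections 6.3.2.1 and 6.3.2.2, so a lung CR can be labelled PR

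*Combined protocol and SAP*

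**What the plan says.** Appendix K sets organ-by-organ criteria. In the Lungs row, the complete-response criterion based on pulmonary function tests (PFTs) is "Normal %FEV1, alkaline phosphatase, and Total bilirubin after previous elevation of 1 or more", with an NIH lung symptom score of 0 as the fallback when PFTs are missing. The Liver row directly above reads "Normal ALT, alkaline phosphatase, and Total bilirubin after previous elevation of 1 or more".

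The other lung cells contain no liver test. Partial response is "Increase by 10% predicted absolute value of %FEV1", progression is the matching decrease, and each has a symptom-score fallback.

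Section 6.3.2.1 states for the lung: "The %FEV1 will be used for response assessment". Section 6.3.2.2 lists %FEV1 as the primary lung measure and, separately, "Liver: bilirubin, alkaline phosphatase, ALT".

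Section 6.3.2.1 says that overall CR "is defined as resolution of all manifestations in each organ or site" and refers to Appendix K only for PR and progression. Section 6.3.2 adds: "The organ-specific and other subcomponents of the overall response score will be analyzed individually and absolute values recorded".

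**The concern.** The lung cell looks like a copying error that became an operative rule. It makes lung CR depend on two liver tests, and it speaks of a previous elevation, although lung involvement shows as a fall in FEV1. No section gives a reason for using liver tests in a lung response.

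Organ-level CR criteria appear nowhere but Appendix K, so an assessor scoring the lung has no other table to use. Two assessors could then score the same patient differently, one from Appendix K and the other from section 6.3.2.1. At stake are the lung result itself and, in some patients, the overall CR-versus-PR call. That call matters at week 12, because section 3.1 sets different next steps for CR and for PR or unchanged disease.

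**Working it through.** The plan states no figure to reproduce here, so the check compares the texts and then works through the thresholds.

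**1. Measures assigned to each organ**

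| Place | Lung | Liver |
|---|---|---|
| 6.3.2.1 | %FEV1 | bilirubin, alkaline phosphatase, ALT |
| 6.3.2.2 | %FEV1 | bilirubin, alkaline phosphatase, ALT |
| Appendix K, PR | %FEV1 up 10 points | down 50% |
| Appendix K, progression | %FEV1 down 10 points | up 2 x ULN |
| Appendix K, CR | %FEV1, alkaline phosphatase and bilirubin all normal | ALT, alkaline phosphatase and bilirubin all normal |

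Only the lung CR cell mixes the two organs.

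**2. Is the cell used?** Exclusion 2.1.2.8 removes lung score 3 only. Appendix D puts score 1 at 60-79% and score 2 at 40-59%, so patients with a reduced FEV1 of 40-79% can enrol. The Study Calendar (3.7) schedules PFTs at weeks 12 and 24, so the PFT branch normally applies. Section 3.6 and calendar footnote 1 allow off-site assessment. PFTs may then be missing, and the fallback, which contains no liver test, applies.

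**3. Who is denied lung CR?** Inclusion 2.1.1.6 allows bilirubin up to 1.5 x ULN, waives that limit for Gilbert's disease, and sets no limit on alkaline phosphatase. A patient can therefore enter with a raised value that has nothing to do with GVHD. If it stays raised, the lung cell is not met even when FEV1 is normal. If instead liver GVHD is the cause, the liver row already bars overall CR and the error affects only the lung label.

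**4. Worked cases.** Appendix K gives no value for normal %FEV1. Assume at least 80%, the Appendix D score-0 line. Suppose alkaline phosphatase stays above normal for a non-GVHD reason.

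- 65% to 82%: gain = 82 - 65 = 17 points. CR on %FEV1 alone. Under the cell, not CR; 17 is at least 10, so PR.
- 71% to 80%: gain = 80 - 71 = 9 points. CR on %FEV1 alone. Under the cell, not CR; 9 is below 10, so not PR either.

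The smallest gain that reaches the line is 80 - baseline. In whole points it is below 10 only for baselines 71-79%. Baselines 40-70% need at least 10 points, so their CR can be relabelled PR but not lost. For any other line T, the exposed baselines are T - 9 to T - 1.

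**5. Effect on the endpoints**

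- *Lung result (6.3.2):* mislabelled whenever step 3 applies and FEV1 normalises.
- *Overall CR:* changed only if every other organ has resolved.
- *24-week CR-plus-PR rate and the 0-of-7 futility count:* unchanged by a CR-to-PR swap. A responder is lost only with a gain under 10 points and no improvement in any other organ.

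**The case against.** The strongest defence is that the body of the protocol is clear. Section 6.3.2.1 names %FEV1, section 6.3.2.2 repeats it, the neighbouring cells agree, and overall CR is defined in words without reference to Appendix K. An assessor may well recognise the slip. Section 6.3.2 also requires absolute values to be recorded, so lung labels can be recomputed. This limits the harm and is why the point rates no higher than moderate. It does not remove the conflict: Appendix K remains the only organ-level CR table, and a step already taken after a week-12 call cannot be recomputed.

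The non-GVHD-cause box in Appendix F, and the rule in Appendix E that leaves such an organ out of global severity, may help in practice. Neither amends the lung cell.

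A PDF reading fault is unlikely. The liver cell is intact, and the lung cell is a complete phrase with one term substituted.

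A reader might infer three stronger things that the documents do not support:

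- *Patients whose liver tests were never raised can never reach lung CR.* This needs elevation to be applied literally to a list that includes %FEV1, where disease is a fall. Reading it as a previous abnormality of at least one listed item is more natural, and a reduced FEV1 meets that.
- *The primary endpoint is biased.* CR and PR both count as response. The exception in step 5 is narrow.
- *The 75% figure in Appendix M is a rival line for normal.* It is one part of a composite bronchiolitis obliterans item that also needs ratio, or volume and CT, findings. It is not a normality threshold.

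The missing value for normal %FEV1 is a separate, secondary matter. The published NIH response criteria that the protocol cites may define it, but they were not available for this check.

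**Conclusion.** The PFT branch of the lung CR cell is wrong as written. This is an internal inconsistency of minor to moderate weight. It can deny lung CR to a patient with normalised %FEV1 and a liver test raised for a non-GVHD reason. The consequences are a mislabelled lung result and, if every other organ has resolved, an overall CR called PR, including at week 12. The 24-week response rate is essentially unaffected.

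The contradiction itself rests on no assumption. The size of its effect rests on two: that assessors apply the cell as printed, and, for the 71-79% range of possible responder loss, that normal means at least 80%. The documents give no rate of lung involvement and no distribution of FEV1 or liver tests, so the number of patients affected cannot be estimated.

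**What to change.** Reconcile the Appendix K lung row with sections 6.3.2.1 and 6.3.2.2:

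1. Reword the PFT branch of lung CR to: normal %FEV1 after previously reduced %FEV1. Delete alkaline phosphatase, total bilirubin and the phrase about previous elevation. Tying the entry condition to reduced %FEV1 also prevents a lung counted as affected on symptoms alone from qualifying through the PFT branch.
2. Keep the symptom-score fallback.
3. Re-derive lung calls already made, and any overall CR or PR call that depends on them, from the recorded %FEV1 values.
4. As a secondary clarification, state which line counts as normal %FEV1 and how a patient who crosses it by fewer than 10 points is scored. The Appendix D score-0 line, at least 80%, is already in the protocol; the choice is the sponsor's.

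The cost is one table cell, one definition and a re-check of existing records. No new data are needed where %FEV1 was measured as scheduled. No change to any dose rule is proposed.

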APPENDIX M: cGVHD NEW PATIENT DATA FORM

Baricitinib for cGVHD (16-C-0094)

New Patient Data Form (Baseline)

Karnofsky Score: _____ **Date on Study:** _____

Disease Characteristic	
Diagnosis	_____

Transplant information:		
Date of transplant	_____	
Type of transplant	 Bone marrow  Bone marrow & PBSC  Cord Blood  Other  Peripheral blood stem cell (PBSC)  Donor Mobilized	
Haploidentical Transplant	 yes  no	
Donor relationship	_____	
Degree of HLA match:	 8/8, 10/10 or 12/12	_____
	 HLA Mismatch	_____
2nd transplant (allo or auto)  Y  N		
Early post transplant events		
Acute GVHD	 Y  N	
DLI	 Y  N	
cGVHD history	Date of cGVHD Diagnosis: _____ GVHD Classification  Classic  Overlap	

Prior Systemic therapy for cGVHD (list all medications/therapies)	
 Tacrolimus  Sirolimus  Cyclosporine  Cellcept  Imatinib  Rituximab  Prednisone  ECP  Anti-thymocyte globulin  Methotrexate  Dacluzimab  Ruxolitinib  Pomalidomide Please list all other therapy previously taken for cGVHD:	
Current Systemic therapy for cGVHD (list all medications/therapies, and add dose just for steroids)	 Y  N
 Tacrolimus  Sirolimus  Cyclosporine  Cellcept  Imatinib  Rituximab  ECP  Ruxolitinib  Methotrexate  Ibrutinib  Pomalidomide  Prednisone (dose) _____ Please list all others:	
Current topical therapy for cGVHD	 Y  N
If yes, list all topical therapy:	
Intensity of current immunosuppression: *see note on bottom of page 3	
 None  Mild (single agent prednisone < 0.5 mg/kg/day)  Moderate (prednisone ≥ 0.5 mg/kg/day and/or any single agent/modality)  High (2 or more agents/modalities ± prednisone ≥ 0.5 mg/kg/day)	

Clinician's impression of activity

- Inactive, off systemic therapy or topical immunosuppression
- Inactive, on systemic therapy or topical immunosuppression
- Active, irrespective of the level of current therapy
- Highly active, irrespective of the level of current therapy

BOS

- Y (1. FEV1<75% and FEV1/FVC ratio <0.7 or 2. FEV1<75% and ratio >_0.7 must have RV or RV/TLC >120% PLUS CT c/w air trapping)
- N

LIP Print Name: _____ LIP
Signature: _____

Date of Evaluation: _____

Timepoint: Baseline _____

* - for "Intensity of current immunosuppression" scale on page 2 just systemic immunosuppression should be considered (PUVA and ursodiol are not systemic immunosuppressive agents, and ECP can be considered as systemic immunosuppressive agent/modality for that scale)
